[figure not shown]
Procedures/Research Design/Methodology/Timeframe

Research Design Aim 1:

Subjects: Patients with dysphagia post stroke will be recruited from the VS-CRF and inpatient and outpatient admissions post stroke. The videofluoroscopic records of patients who volunteer will be reviewed to determine if they have a score of 2 or greater on the Pen-Asp scale⁴⁷. Those without a videofluoroscopic study will receive the Mann Assessment of Swallowing Ability to identify those with a severity rating of “mild” or greater, that is a total numeric score of 177 or less^{48,49}. If a nasoendoscopic evaluation of swallowing has been conducted, that will also be reviewed to determine if there is evidence of risk of aspiration⁵⁰. (see Human Subjects protection).

i. Frequency Comparisons:

Motors at frequencies of 30, 70, 110, 150, and 70/110 Hz (using 2-6 kPa neck pressure) will apply 8 s of stimulation followed by 15 s rest for a total of 28 stimulation trials for a total of 10.7 minutes per condition. Optionally, other hybrid motors similar to the 70/110 Hz motor may be used. After a condition, the patient will mark on a visual analogue scale of 0 to 100 mm their *urge to swallow* and their comfort level with stimulation for that condition. Online recordings of bi-axial accelerometry of laryngeal motion, inductive plethysmography of respiration, and digital video recordings will identify laryngeal movement and respiratory apnea

[figure not shown]

to confirm swallows (Figure 4). Swallows cannot be identified during stimulation because of vibration interfering with the accelerometry signals, which necessitates video recording. The *rate of swallowing* in a 10.7 minute condition will be computed. The order of different frequencies will be counter-balanced across patients. Total testing time with rest periods will be 1 hour. If all the frequencies cannot be tested in the one hour time period, the remaining untested frequency (ies) can be completed at the end of another session if time allows, or the participants can attend additional sessions as needed. We expect that one frequency will be optimal across patients; if two frequencies are optimal we will combine them by using motors with different frequencies on each side.

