ii. Mode Comparisons: Using the optimal frequency(ies) identified, we will compare the effects of continuous versus the 4 Hz pulsed modes for 10.7 minutes each in counter-balanced order across patients measuring the rate of swallowing and ratings of the urge to swallow to identify the most effective mode of stimulation.

iii. Pressure Comparisons: Using the Iowa Oral Performance Instrument to measure strap to neck pressure and calipers to measure neck tissue fat, the effects of 2, 4, and 6kPa on rate of swallowing and urge to swallow with 8 s stimulation at the optimal frequency and mode of stimulation will be measured.

iv. Stimulation Duration: We will determine the stimulation durations applied by patients when they are instructed to initiate swallowing during stimulation using the parameters identified for stimulation in i, ii and iii. The time required for them to

[figure not shown]
initiate swallowing after the onset of stimulation will be measured using air filled bellows wrapped around the neck to identify swallowing timing after stimulation onset (Figure 5). Air filled bellows are required as vibratory stimulation will interfere with accelerometry; we have used these bellows previously to identify swallowing in fMRI⁴². Additionally oral pressure sensor in using a small tube placed on the anterior tongue will may be used to identify swallows. Neck calipers will measure tissue thickness in the throat area overlying the thyroid cartilage which may affect sensory input. When the participant has completed their final session, they will mark on a visual analogue scale of 0 to 100 their level of interest in using the self-training device at home for swallowing therapy.

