Assignment to Studies. Participants will be recruited into the studies planned for Aim 1 in the order that we conduct the studies. The first study, study i, will compare the effects of motors at frequencies of 30, 70, 110, 150, 70/110 Hz, and other similar hybrid motors and measure the degree of *urge to swallow*, comfort level and frequency of swallowing during intervals following stimulation. To identify swallowing, noninvasive recordings will involve of bi-axial accelerometry of laryngeal motion, inductive plethysmography of respiration, and video recordings will identify laryngeal movement and respiratory apnea to confirm swallows. Total testing time for this first study will not exceed 1 hour; if a participant becomes fatigued we will stop the testing. Fifteen participants will be recruited and tested to evaluate different motor frequencies in study i. The testing for study ii comparing continuous versus pulsed stimulation will be conducted along with study iv determining how long stimulation is needed for a participant to initiate swallowing after stimulation, as these two studies combined will require about 1 hour. These studies will also involve 15 participants, some of who may have participated in study i. Finally, study iii will also require no more than 1 hour and will compare the effects of different neck band pressures in 15 participants some of whom may have participated in studies i, ii or iv.

We will try to accommodate participants' needs and prevent fatigue or inconvenience by dividing up the testing conditions or conducting the testing in their home if they prefer. All of our equipment is portable, including suctioning, which will allow us to travel to the participants' environments either at home, or in a nursing or rehabilitation setting. Only nasoendoscopy is restricted to the hospital environment and will only be conducted if ordered by a physician.

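### Study iv (duration) is to run at the pressure chosen in study iii, but the order of conduct puts study iii after study iv

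*Protocol*

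**What the plan says.** The Aim 1 research design in the Protocol is a chain of four experiments. Study i compares motor frequencies, "using 2-6 kPa neck pressure". Study ii compares continuous with pulsed stimulation at the chosen frequency, "measuring the rate of swallowing and ratings of the urge to swallow to identify the most effective mode of stimulation". Study iii compares 2, 4 and 6 kPa of neck pressure at the chosen frequency and mode. Study iv measures how long stimulation lasts before a swallow, "using the parameters identified for stimulation in i, ii and iii".

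The order of conduct is set in the Assignment to Studies paragraph of the human subjects section. It opens: "Participants will be recruited into the studies planned for Aim 1 in the order that we conduct the studies". It calls study i the first study. It continues: "The testing for study ii comparing continuous versus pulsed stimulation will be conducted along with study iv", because the two together take about an hour. It ends: "Finally, study iii will also require no more than 1 hour and will compare the effects of different neck band pressures". The sample for that last study is again 15, and the paragraph describes the group as people "some of whom may have participated in studies i, ii or iv".

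**The concern.** Study iv depends on the output of study iii, yet study iii is scheduled after it. A team following the order of conduct would have to choose a pressure for study iv without the result that the design section says to use. The protocol names no substitute.

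This matters because study iv is the only experiment that measures duration, and Importance of the Knowledge to be Gained lists duration among the characteristics this trial will settle for the Phase II device. A duration measured at one pressure, and possibly one mode, could be carried into a device built with another. The protocol itself treats pressure as possibly influential: study iii exists to test its effect on swallowing rate and urge to swallow.

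**Working it through.** **The plan's own figure.** Expected Outcomes and Power Analyses gives 15 patients per experiment. Inputs: a change from 1.2 to 2.0 swallows per minute, SD of differences 0.9, alpha 0.025, power 0.80, stated effect size 0.88 (0.8 / 0.9 = 0.889). Sidedness is not stated. A paired t-test with two-sided alpha 0.025 needs n = 15, with power 0.803 at 0.88 and 0.812 at 0.889. The figure reproduces, and nothing below depends on it.

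**The two orders side by side.**

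| Study | Result it needs (Aim 1 design) | Place in the order (Assignment to Studies) |
|---|---|---|
| i, frequency | none | first |
| ii, mode | i | second, together with iv |
| iii, pressure | i, ii | last |
| iv, duration | i, ii, iii | second, together with ii |

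The design needs i, ii, iii, iv. The order of conduct is i, (ii + iv), iii.

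**Settings available when study iv is run.**

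- *Frequency:* available, because study i is complete.
- *Pressure:* not available. The sections on ii and iv give no value of their own. The range in study i covers 2, 4 and 6 kPa, so it selects none of them.
- *Mode:* probably not available. The power section compares mean scores and mean rates across conditions with 15 patients per experiment, which points to a group decision after study ii is complete. Swallows are confirmed on video at the analysis stage (Sources of materials). Of frequency, the protocol says: "We expect that one frequency will be optimal across patients". No sentence says outright that mode is a group decision. A choice for each participant from the urge ratings in the session is not excluded, since study ii takes 2 x 10.7 = 21.4 minutes of a session of about 60.

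So of three required settings, one is available, one is not, and one probably is not.

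**Could study iii simply move forward?** No. It needs the mode from study ii, and study ii is tied to study iv. Placing iii before the ii + iv session removes one conflict and creates another.

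**The case against.** The strongest reply is that the order is inferred. The word that introduces study iii can close a list as well as mark time, the pairing of ii and iv is explained by session length, and participants may take studies in flexible visits. The paragraph's first sentence, the label given to study i, and the remark that study iii participants may already have been in study iv make the chronological reading clearly the better one. Flexible visits do not supply a pressure result.

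A second reply is that the mode point is not proved. That stands, and mode is counted here only as probable. The contradiction on pressure holds without it.

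A third is that the consequence is thin. The list of device characteristics in Importance of the Knowledge to be Gained names the strap but not pressure, the study iii text speaks of measuring effects rather than selecting a level, and nothing links pressure to the time taken to swallow. This stands in part: the size of any shift is unknown. But the study iv text treats pressure as something identified in study iii, and the human subjects section names pressure among the device characteristics on which participants' preferences are sought.

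The mismatch may come from a human subjects section that was revised without realigning the design section. That could explain it, but both texts are current and both instruct the study team.

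**Conclusion.** The concern holds. For pressure, the study iv text and the Assignment to Studies paragraph cannot both be followed. All 15 study iv participants are affected, through one setting for certain and a second probably.

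The conclusion assumes that the Assignment to Studies paragraph is chronological. The mode part further assumes that mode is chosen on group data. The document gives no figure relating pressure or mode to time to swallow, so the effect on the duration result could be nil or material and cannot be estimated. Studies i to iii and the sample size are untouched. It should be fixed before study iv starts, because it bears on the only duration result passed to Phase II.

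**What to change.** Reconcile the two sections in one of two ways. The choice, and any setting used, belongs to the investigators.

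**(a) Change the order of conduct.** Separate study iv from study ii and run it once ii and iii are decided. This keeps the intent of the design section. Cost: up to 15 extra short sessions, 15 x $20 = $300, plus mileage at a rate the protocol does not give. If settings are decided on group data, a participant in all four studies needs at least 4 visits, which fits the three or more visits under Potential Risks. Participant slots rise from 3 x 15 = 45 to 4 x 15 = 60, so returning participants must fill at least 15 more slots than now: from 0 to 15 with 45 recruits, 5 to 20 with 40, or 15 to 30 with 30. Whether people can be kept that long cannot be computed, because no dates per study are given. Stated participation is about 1 month in one place and 1-2 months in another.

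**(b) Change the study iv text.** Keep the pairing with study ii, state that study iv uses one mode and one pressure fixed in advance for everyone, and limit the duration conclusion to those settings. This costs only wording, but Phase II may then have no duration measured at the settings finally selected, and the protocol should say so.

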Expected Outcomes and Power Analyses: For each of the 4 experiments we will compare the mean visual analogue score and the mean swallowing rate within patients across conditions. Based on previous studies in healthy volunteers contrasting air puff stimulation on the rate of swallowing by Theurer et al.,^{38, 51}, the expected change in rate of swallowing will be from 1.2 swallows/minute without stimulation to 2.0 with stimulation with a standard deviation of the differences being 0.9. Using a Bonferroni corrected alpha of 0.025 (to test 2 measures) at 0.80 power with an effect size of 0.88, the number of patients needed will be 15 per experiment. Allowing for some patients to participate in several studies, we plan to recruit between 30 and 40 patients with risk of aspiration post stroke to participate in Aim 1 (see Human Subjects section).

Potential Problems and Alternative Strategies: Anticipated problems include difficulties with recruiting an adequate sample of patients in the Harrisonburg area for testing in our clinic at RMH. Over 412 patients were admitted to RMH acute post stroke in 2010 and the number is increasing each year while many more come for outpatient rehabilitation. We have 3 rooms in our JMU-RMH VS-CRF to support multiple patients being tested simultaneously. All equipment can be portable including Powerlab, a laptop, the amplifier system, the Kistler accelerometers and Inductive plethysmography so we can also test patients in rehabilitation and skilled nursing facilities throughout the Shenadoah valley. The 2011 Healthy Community Survey found that 20 percent of seniors in the Harrisonburg area have had a stroke out of an estimated 120,000 total population. Therefore access to 40 post stroke patients with dysphagia is feasible. In addition, we have developed a website, NetMedSLP, serving speech pathologists in medical settings throughout Virginia. This site provides continuing education to speech pathologists specializing in dysphagia in Virginia. Over 2 dozen speech pathologists are registered and we intend to use this website to recruit collaborating speech pathologists for patient referral for our research studies. Further, Passy Muir employs 2 respiratory therapists in Virginia who can access speech pathologists to assist with patient recruitment. Future Directions These studies will be the basis for designing a prototype device for swallowing retraining by patients with dysphagia post stroke for Phase II.

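### The 15 patients per experiment and 0.80 power are calculated for stimulation versus no stimulation, a contrast that none of the four Aim 1 experiments makes

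*Protocol*

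**What the plan says.** The paragraph on expected outcomes and power under Research Design Aim 1 of the Protocol opens with a general statement: "For each of the 4 experiments we will compare the mean visual analogue score and the mean swallowing rate within patients across conditions". It then takes its planning figures from air-puff studies in healthy volunteers: "the expected change in rate of swallowing will be from 1.2 swallows/minute without stimulation to 2.0 with stimulation", with an SD of the differences of 0.9. The calculation follows: "Using a Bonferroni corrected alpha of 0.025 (to test 2 measures) at 0.80 power with an effect size of 0.88", leading to 15 patients per experiment. The section on recruitment and informed consent repeats that 15 participants in each of the four studies give adequate statistical power.

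The experiments themselves are described as follows.

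- **i, Frequency Comparisons:** five motor types (30, 70, 110, 150 and 70/110 Hz). Each condition consists of "8 s of stimulation followed by 15 s rest for a total of 28 stimulation trials". More motors are possible: "Optionally, other hybrid motors similar to the 70/110 Hz motor may be used".
- **ii, Mode Comparisons:** "we will compare the effects of continuous versus the 4 Hz pulsed modes for 10.7 minutes each".
- **iii, Pressure Comparisons:** "the effects of 2, 4, and 6kPa on rate of swallowing and urge to swallow".
- **iv, Stimulation Duration:** the setting chosen from i to iii is applied, and the time from stimulation onset to swallow is measured.

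**The concern.** A sample size supports a power claim only for the contrast it was calculated for. Here the planned effect is the gain from having stimulation at all, while the experiments ask which of several active settings works best. The expected difference between two active settings, and its SD, are different quantities, and the protocol gives neither.

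Experiment iv raises a further contradiction. The power paragraph includes it among four experiments that compare swallowing rate across conditions. Its own description has a single setting and an onset-time outcome.

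At stake is what the ethics board and the device developers are told. According to the section on the importance of the knowledge to be gained, the results decide motor type, frequency, mode and duration for the Phase II device. Experiments ii, iii and iv also build on settings chosen earlier in the sequence. A reader would take it that each comparison behind those choices has 0.80 power, and the calculation does not show this.

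**Working it through.** **Inputs from the Protocol (power paragraph).** Difference 2.0 − 1.2 = 0.8 swallows/min; SD of differences 0.9; alpha 0.025 (0.05/2 for two measures); power 0.80; n = 15. Sidedness is not stated.

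**Step 1: reproduce the stated figure.** Effect size d = 0.8/0.9 = 0.889, given as 0.88. For a paired t-test the noncentrality is d√n on n − 1 degrees of freedom. With n = 15 and d = 0.88 this is 0.88 × √15 = 3.41, against a two-sided critical value of 2.51 on 14 df. Power is 0.803; at n = 14 it is 0.766. So 15 is the smallest n that reaches 0.80. A one-sided test at 0.025 would need only 13, so the calculation was evidently two-sided.

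**Step 2: look for the contrast in the design.**

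| Experiment | Conditions | Unstimulated condition? |
|---|---|---|
| i | five motors (hybrids optional) | none |
| ii | continuous, 4 Hz pulsed | none |
| iii | 2, 4, 6 kPa | none |
| iv | one chosen setting, onset time | none, and no second condition |

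The 15 s rests in i are not a baseline. They occur within every active condition, the rate is computed over the whole 10.7 minutes, and the section on assignment to studies counts swallows in the intervals after stimulation as part of the outcome.

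**Step 3: what n = 15 gives for two active settings.** The difference is an assumption, because the protocol gives none. Keeping SD 0.9 and two-sided alpha 0.025, the noncentrality is (difference/0.9) × √15:

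| Difference (swallows/min) | d | Power, n = 15 | n for 80% power |
|---|---|---|---|
| 0.2 | 0.222 | 0.07 | 195 |
| 0.4 | 0.444 | 0.25 | 51 |
| 0.6 | 0.667 | 0.54 | 24 |
| 0.8 | 0.889 | 0.81 | 15 |

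The difference detectable with 80% power is 0.876 × 0.9 = 0.79/min. That is 0.79/0.8, or about 99%, of the assumed effect of stimulation over none.

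**Step 4: sensitivity to the SD.** At a difference of 0.4/min, power is 17% for SD 1.1, 25% for SD 0.9, 54% for SD 0.6 and 81% for SD 0.45. Two active settings in the same patient may well give a smaller SD of differences than 0.9, so the low figures are not certain. The 0.80 is equally unsupported.

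**The case against.** The strongest defence is that this is a Phase I device-selection study. The statement of purpose says usefulness is not being evaluated, and the aim is to find the best setting: "We expect that one frequency will be optimal across patients". Choosing a setting does not require a significant difference, and urge ratings and preferences count as well as swallowing rate. This stands, and it limits the practical harm. It does not rescue the sentence, because the protocol itself presents 15 as the number that gives 0.80 power at a corrected alpha.

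A reader might go further and infer that alpha 0.025 should have been divided over the 10 pairs of five motors or the 3 pairs of pressures. Power at 0.79/min would then fall to 43% and 63%. The protocol does not support this reading. It says only that means are compared within patients across conditions, and it adopts no all-pairs testing. A repeated-measures F-test at 0.025 fits that wording at least as well. With one setting better than equal others, SD 0.9 for every pair, and sphericity, it has about 87% power for three pressures and 88% for five motors at the same 0.79/min, although it answers only whether any difference exists.

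A reader might also want the power replaced by a probability of picking the best setting. That depends on a rule the protocol does not use, namely one winner on rate alone. Experiment i allows two optimal frequencies to be combined, and urge ratings also enter. The result is also fragile. For five motors it is about 87% if one is 0.4/min better than four equal others, but 57% if the motors are graded in steps of 0.1/min over the same range.

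**Conclusion.** Wrong as written. The calculation is arithmetically sound, but its 0.80 power belongs to a contrast that no experiment makes. For a single pair of active settings it holds only if they differ by about 0.79 swallows/min at SD 0.9, and the protocol offers no support for that. At half the planned effect, 0.4/min, power is 25% at SD 0.9 and ranges from 17% to 81% over SDs of 1.1 to 0.45. For iv the power claim does not apply at all, and its inclusion in a rate comparison across conditions contradicts its own description.

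These figures rest on a two-sided paired t-test on swallowing rate and on an SD borrowed from healthy volunteers given a different stimulus. They do not show that 15 is too few for choosing a setting, nor that a particular multiplicity correction was owed. The harm is moderate: the stated justification misleads, while the selection purpose is less demanding than a test at 0.80 power.

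**What to change.** In the power paragraph, replace the power claim with text such as:

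> With 15 patients, alpha 0.025 (two-sided) and an assumed SD of within-patient differences of 0.9 (from healthy volunteers given air puffs), a paired comparison of two active settings on swallowing rate has 80% power for a difference of 0.79/min, about 54% at 0.6/min and 25% at 0.4/min. At 0.4/min, power ranges from 17% (SD 1.1) to 81% (SD 0.45).

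Alternatively, call 15 a feasibility or estimation size and make no power claim.

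In either case, state that iv is descriptive (time to swallow onset). Remove it from the sentence that has all four experiments comparing swallowing rate across conditions, and from the adequate-power statement in the recruitment section. Leave all-pairs Bonferroni figures and correct-selection probabilities out of the replacement text, since the protocol adopts neither method.

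The cost is rewording in two places and a less favourable stated power. No patients, sessions or recordings are added.

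### Holm's step-down rule would keep the same 5% error control over the two measures and never lose power against the stated Bonferroni 0.025: an optional improvement, not the correction of an error

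*Protocol*

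**What the plan says.** Under Research Design Aim 1, the paragraph on expected outcomes and power sets the comparison for the experiments: "we will compare the mean visual analogue score and the mean swallowing rate within patients across conditions". There are thus two measures, each analysed within patients. The same paragraph takes the expected swallowing rate "from 1.2 swallows/minute without stimulation to 2.0 with stimulation", "with a standard deviation of the differences being 0.9". It handles the two measures with a single-step correction: "Using a Bonferroni corrected alpha of 0.025 (to test 2 measures) at 0.80 power with an effect size of 0.88". From this it concludes that "the number of patients needed will be 15 per experiment".

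The Mode Comparisons paragraph (ii) shows the two measures in use, "measuring the rate of swallowing and ratings of the urge to swallow to identify the most effective mode of stimulation". The Protocol mentions no step-down or other sequential rule for the two tests. It does not say whether the tests are one- or two-sided, and it gives neither an effect size for the visual analogue score nor a correlation between the two measures.

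**The concern.** Single-step Bonferroni holds both tests at 0.025 whatever the other one shows. Once one of two hypotheses has been rejected at 0.025, the remaining one can be tested at the full 0.05 without exceeding 5% familywise error. That is Holm's rule for two tests. Under Bonferroni, a second measure with a p-value between 0.025 and 0.05 is called non-significant even when the first is already significant, and the error control does not require this.

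What is at stake is some power on the measure with the larger p-value, in experiments of only 15 patients. The Protocol itself lists recruitment as an anticipated problem, so power that costs no patients is worth considering. The validity of the tests is not at stake, and neither is the sample size.

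**Working it through.** **Inputs from the Protocol (Expected Outcomes and Power Analyses).** Mean change 2.0 − 1.2 = 0.8 swallows/minute; SD of differences 0.9; stated effect size 0.88 (0.8/0.9 = 0.889); alpha 0.025 per measure, so 0.05 over two; power 0.80; n = 15.

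**Assumptions.** Two-sided paired t-tests on two conditions. Two-sided testing is assumed because it returns the stated 15; one-sided 0.025 would need 12 or 13. The visual analogue effect is set to 0.88, 0.5, 0.3 or 0, and the correlation between measures to 0 to 0.6.

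**Step 1: reproduce the 15.** Power is P(|T| > c), with T noncentral t on n − 1 degrees of freedom and noncentrality d√n.
- n = 15, d = 0.88: noncentrality 0.88 × √15 = 3.41. At two-sided 0.025, c = 2.510 and power is 0.8035. At n = 14 it is 0.766. So 15 is correct.
- With d = 0.889, n is again 15 (power 0.812).
- At two-sided 0.05, n = 15, d = 0.88: c = 2.145 and power is 0.8863.

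**Step 2: Holm by hand, correlation 0.** Measure 1 is significant if p1 ≤ 0.025, or if 0.025 < p1 ≤ 0.05 and p2 ≤ 0.025. With independent measures:

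Holm power for measure 1 = B1 + (F1 − B1) × B2, where B is power at 0.025 and F is power at 0.05.

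- Both effects 0.88: 0.8035 + (0.8863 − 0.8035) × 0.8035 = 0.870.
- Both 0.5 (B = 0.3169, F = 0.4379): 0.3169 + 0.1210 × 0.3169 = 0.355.
- Both 0.3 (B = 0.1194, F = 0.1915): 0.1194 + 0.0721 × 0.1194 = 0.128.
- Rate 0.88, visual analogue score null (B2 = 0.025): 0.8035 + 0.0828 × 0.025 = 0.806.

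Power for at least one measure, both 0.88: 1 − (1 − 0.8035)² = 0.961 under either rule, because the first rejection always needs a p-value of at most 0.025.

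**Step 3: correlation 0 to 0.6.** Simulation of two correlated paired t-tests at n = 15, at least 200,000 runs per scenario:

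| Effects (rate, visual analogue) | Quantity | Bonferroni | Holm |
|---|---|---|---|
| 0.88, 0.88 | power per measure | 0.80 | 0.86-0.87 |
| 0.88, 0.88 | both significant | 0.65-0.70 | 0.78-0.80 |
| 0.88, 0.88 | at least one | 0.91-0.96 | 0.91-0.96 |
| 0.5, 0.5 | power per measure | 0.32 | 0.36 |
| 0.3, 0.3 | power per measure | 0.12 | 0.13-0.14 |
| 0.88, 0.5 | visual analogue power | 0.32 | 0.41-0.42 |
| 0.88, 0 | swallowing-rate power | 0.80 | 0.80-0.81 |
| 0.88, 0 | false positive on visual analogue | 0.025 | 0.043-0.046 |
| 0, 0 | familywise error | at most 0.05 | at most 0.05 |

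Holm is never below Bonferroni, and its error stays within 5% in every row.

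**The case against.** **Nothing is stated wrongly.** Bonferroni at 0.025 is valid and the 15 is right for its inputs. This stands in full, and it is why the point is optional.

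**The sentence is a sample-size statement.** Sizing at Bonferroni and analysing with Holm are compatible, and an analysis plan not shown here may already set the final testing rule. This also stands. Still, the Protocol does name 0.025 as the level for testing the two measures, so a sentence here is a reasonable place to settle it.

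**The large gain is a favourable case.** The 0.88 is stimulation against no stimulation, for swallowing rate only, from healthy volunteers given air puffs. Studies i to iii compare active settings with each other, where differences may well be smaller. A two-condition calculation matches only the design of study ii, and 0.88 is optimistic even there. This stands: at effects of 0.3 to 0.5 the per-measure gain is about 1 to 4 points.

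**Holm gives up matching intervals.** Under Bonferroni, the test and the 97.5% interval always agree. Under Holm, a second measure with p = 0.04 would be significant while its 97.5% interval includes zero. This is a real, small cost, and preferring consistent intervals in a small device-setting study is defensible.

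**A stronger reading is tempting.** A reader might infer that a setting is chosen only if both measures are significant, so that Bonferroni creates false disagreement between rate and urge. The Protocol does not say so: it uses both measures to find the best setting but never makes joint significance the rule. If it did, each measure could be tested at 0.05 without adjustment (both significant in 0.79-0.82 of trials at effects of 0.88, slightly above Holm). If either measure sufficed, Holm would gain nothing. Holm helps where a separate conclusion on each measure is wanted.

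**Conclusion.** The efficiency point holds as an optional improvement. Holm gives the same 5% familywise control over the two tests and is never less powerful than the stated rule. The per-measure gain is about 6 to 7 points if both effects are 0.88, about 4 points if both are 0.5, and 1 to 2 points if both are 0.3. These figures are for a two-condition paired comparison at n = 15 with correlation 0 to 0.6. The visual analogue effect and the correlation are assumptions, so only a range can be given.

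The gain falls only on the measure with the larger p-value. Under either rule, the 5% covers two tests in one experiment; it does not extend to pairwise comparisons among the five frequencies of study i or the three pressures of study iii. A reader should not conclude that the Bonferroni correction or the 15 patients is an error.

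**What to change.** Keep the sample size as computed at 0.025. Add one sentence to the power paragraph for Aim 1: within each experiment that tests both measures, the smaller p-value is compared with 0.025 and, only if it is significant, the larger with 0.05. Report 97.5% intervals for both measures, and note that a second measure with a p-value between 0.025 and 0.05 can be significant while its 97.5% interval includes zero.

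The cost is that sentence and note, fixed before the data are analysed. No patients, visits or measurements are added. The price is the occasional mismatch between test and interval.
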